6.1 Extent of Exposure

The exposure to each study drug will be summarized in terms of:

- Number of started cycles
- Total cumulative dose

6.2 Adverse Events

Frequency and severity of adverse events categorized using the NCI Common Terminology Criteria for Adverse Events version [4.0 (CTCAE v4.0)] will be tabulated. The adverse events are coded using MedDRA Version [18.1]. AE rates will be described by dose level without regard to attribution. Treatment Emergent Adverse events (TEAEs) will be analyzed in terms of their type, incidence and severity. An adverse event is treatment emergent if it occurs on or after the date of the first administration of study drug. According to the protocol, only treatment emergent AEs are collected on this study.

A summary table including the number of AEs and the number of patients with at least one:

- AE
- Grade 1/2 AE
- Grade 3 or 4 AE
- Serious AE
- AE leading to permanent discontinuation of either one of both study treatments
- Fatal AE
- AE leading to death

will be presented.

Tabulations of the number of patients who experienced treatment emergent adverse events as well as grade of the events will be presented by system organ class and preferred term. Patients will only be counted once for each preferred term. In case a patient experienced the same event more than once, the worst grade will be presented.

Listings of all AEs detailing all AE information by patient with flags for SAE, AE leading to treatment discontinuation, Fatal AE, and AE leading to death.

6.3 Deaths

The number of deaths will be tabulated together with the primary cause of death. The details of the 'other will be included in the listing.

7. Efficacy Analysis

The efficacy analyses will use data from tumor assessments for all subjects at baseline and then after every 2 cycles (8 weeks) of treatment. The overall response to the treatment is classified as Complete Response (CR), Partial Response (PR), Stable Disease (SD) or Progressive Disease (PD) and is recorded in the eCRF at each tumor assessment.

7.1 Primary Analysis of Stage II: Objective Response Rate

The ITT population will be used to test the effects of therapy on ORR. The best overall response is the best response recorded from the start of the treatment until disease progression/recurrence (taking as reference for progressive disease the smallest measurements recorded since the treatment started). Confirmation of complete or partial response IS NOT required.

A summary table presenting % of patients with a best overall response of CR, PR, SD and PD will be made. ORR will be calculated as % of patients with CR or PR at any time during the treatment (including unscheduled assessments). The 95 % confidence interval of the ORR proportion will be reported using exact method based on the binomial distribution (Clopper-Pearson method). The denominator will be the number of patients in the ITT population.

The primary objective of the trial will be reached if at least 3 responses are observed among 21 evaluable patients (14.3%).

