2.9 Translational opportunities

Pre-clinical and clinical data suggest that combination of immune checkpoint inhibitors targeting non-overlapping pathways such as durvalumab and tremelimumab may induce synergistic effect leading to improved tumor response in comparison to monotherapy with either agent alone. We hypothesize that the combination of radiation and dual immune checkpoint blockade with durvalumab plus tremelimumab may have synergistic effect on effector T cell activation ([Pardoll 2012](#)).

This study serves as a platform allowing for detailed assessment of the mechanisms of immune stimulation, predictive markers of response or resistance and rational development of the next generation of combination immunomodulatory interventions ([Taube 2014](#), [Topalian 2012](#)). Samples will be collected that may be used in post-hoc analyses including but, not limited to:

- peripheral lymphocytes analysis for immune cell gene expression and quantitative changes of lymphocyte subpopulation and immune-related cells.
- collection of tumor tissues from unirradiated tumor sites prior to radiation and after two cycles of therapy for further analysis of immune response in tumor.
- analysis of gene expression related to immune checkpoint pathways.
- analysis of frequency of mutation-associated neoantigens in tumor tissues.

3.0 **STUDY AIMS AND ENDPOINTS**

3.1 **Primary aim and endpoint**

Aim: To determine the efficacy of the dual immune checkpoint blockade with durvalumab plus tremelimumab following a small dose of hypofractionated palliative radiation in patients with MSS mCRC who have progressed on chemotherapy.

Endpoint: Overall objective response rate (ORR) as measured by RECIST 1.1 criteria.

3.2 **Secondary aims and endpoints**

3.2.1 ***Clinical benefit rate***

Aim: To determine objective tumor decrease and stable disease (SD) at 16 weeks.

Endpoint: Measurement of disease status by continuous tumor measurement (any partial response [PR], any complete response [CR] and SD at 16 weeks).

3.2.2 ***Duration of response***

Aim: To determine the duration of response of mCRC to study therapy.

Endpoint: Measurement of time from study entry until documentation of progression as determined by RECIST 1.1.

3.2.3 ***Safety and Toxicity***

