8.2 Treatment management for durvalumab and tremelimumab

The study treatment schedule should be maintained. If necessary, the timing of a treatment may be adjusted to 3 days earlier or 3 days later than the scheduled date of treatment. All doses administered or missed must be recorded.

8.2.1 *Treatment decisions when therapy must be held*

- In the event systemic steroid therapy is initiated for toxicity management, study therapy must be held. The steroid taper should be completed within 28 days. Study therapy may then be resumed after completion of the steroid taper on Day 1 of the next scheduled cycle.
- Note: Should the steroid taper require a slower rate for completion (i.e., > 28 days), further study therapy doses must be discontinued.
- See [Table 7](#) for treatment management.

8.2.2 *Treatment decisions when therapy must be discontinued*

Treatment must be discontinued if:

- If either durvalumab or tremelimumab must be held for > 28 days of continuous delay for other than steroid taper (e.g., toxicity).
- Consent is withdrawn or patient is lost to follow-up. If consent is withdrawn, the patient will not receive any further investigational product or further study observation.
- An adverse event occurs that, in the opinion of the investigator or sponsor, contradicts further dosing.
- The patient becomes pregnant or intends to conceive a child while actively on study.
- Grade 3 or greater infusion reaction occurs.
- Bullous rash.
- Diagnosis of Guillain-Barre and/or Myasthenia Gravis.
- Initiation of alternate cancer therapy including another investigational agent.
- If tumor progression occurs during study therapy, durvalumab must be discontinued. See [Section 11.0](#).

See [Table 7](#) for additional treatment management requirements. Patients who prematurely discontinue study therapy should complete assessments on [Table 2](#).

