11.0 ASSESSMENT OF EFFECT

Response to study treatment in this patient population will follow standard RECIST criteria except in the documentation of progressive disease (PD). In this protocol, patients with progressive radiographic metastatic disease who are clinically asymptomatic and without other significant reason to discontinue therapy (i.e., toxicity, physician's judgement or patient's decision to stop therapy) may continue to receive study therapy per protocol until the next scheduled tumor assessment ([Table 2](#)) to confirm progression. If progression is confirmed the date of progression will be at the time of the initial scan indicating progression.

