11.2 Response criteria

11.2.1 *Evaluation of target lesions*

- *Complete response (CR)*
Disappearance of all target lesions
- *Partial response (PR)*
At least a 30% decrease in the sum of the of LD of target lesions, taking as reference the baseline sum LD

- *Progressive disease (PD)*
At least a 20% increase in the sum of the LD of target lesions, taking as reference the smallest sum LD recorded since baseline or the appearance of one or more new lesions
- *Stable disease (SD)*
Neither sufficient shrinkage to qualify for PR nor sufficient increase to qualify for PD, taking as reference the smallest sum LD since baseline

11.2.2 *Evaluation of non-target lesions*

- *Complete response (CR)*: disappearance of all non-target lesions,
- *Incomplete response/stable disease (SD)*: persistence of one or more non-target lesion(s).
- *Progressive disease (PD)*: Appearance of one or more new lesions and/or unequivocal progression of existing non-target lesions.

11.2.3 *Evaluation of best overall response*

The best overall response is the best response recorded from the start of the treatment until disease progression/recurrence (taking as reference for progressive disease the smallest measurements recorded since the treatment started).

Refer to [Table 8](#) for a summary of the criteria that contribute to the determination of response.

Table 8. Determination of response

Target Lesions	Non-Target Lesions	New Lesions	Overall Response
CR	CR	No	CR
CR	Incomplete response/SD	No	PR
PR	Non-PD	No	PR
SD	Non-PD	No	SD
PD	Any	Yes or No	PD*
Any	PD	Yes or No	PD*
Any	Any	Yes	PD*

*Confirmation of PD in a patient with new lesion(s) or suspected tumor flare is required as outlines in [Sections 11.2.1](#) and [11.2.2](#).

11.3 **Symptomatic deterioration**

Patients with a global deterioration of health status requiring discontinuation of treatment without objective evidence of disease progression at that time should be reported as "symptomatic deterioration." This is also true for "symptomatic deterioration" after therapy is completed. Every effort should be made to document objective progression even after discontinuation of treatment.

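### SAP 7.1 uses two response windows for the primary endpoint, so a CR or PR after an unconfirmed PD scan can be scored two ways

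*Combined protocol and SAP*

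**What the plan says.** **Response.** Protocol 3.1 names the primary endpoint: "Overall objective response rate (ORR) as measured by RECIST 1.1 criteria". SAP 7.1 then gives two windows in adjacent paragraphs. For best overall response: "The best overall response is the best response recorded from the start of the treatment until disease progression/recurrence", the same window as protocol 11.2.3. For the endpoint itself: "ORR will be calculated as % of patients with CR or PR at any time during the treatment (including unscheduled assessments". The second has no cut-off at progression. SAP 7.1 also says "Confirmation of complete or partial response IS NOT required", so a single scan settles whether a patient is a responder.

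**Progression.**
- Section 11.0: "Response to study treatment in this patient population will follow standard RECIST criteria except in the documentation of progressive disease (PD". Clinically asymptomatic patients with no other reason to stop "may continue to receive study therapy per protocol until the next scheduled tumor assessment". If progression is confirmed it is dated to the first scan. Nothing is said about progression that is not confirmed.
- Sections 11.2.1 and 11.2.2 define PD on one assessment and contain no confirmation rule.
- The Table 8 footnote: "Confirmation of PD in a patient with new lesion(s) or suspected tumor flare is required". For the rule it cites 11.2.1 and 11.2.2.
- Section 8.2.2: "If tumor progression occurs during study therapy, durvalumab must be discontinued", followed by a pointer to Section 11.0.

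**Decision rule.** Protocol 14.2 stops the trial at 0 responses among 12 evaluable patients, rejects the combination at 2 or fewer of 21, and considers it further at 3 or more.

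**The concern.** A trial that allows treatment past a first PD scan can record a response after that scan, and the Table 8 reference to tumor flare suggests that the authors had this in mind. The plan then needs one sentence saying whether such a response counts. SAP 7.1 instead has one sentence that can exclude it and one that includes it, and the protocol does not settle whether an unconfirmed PD scan is progression.

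Both decision points turn on a single patient. The study is open label, so an unfixed rule would be chosen by people who already know which patients it affects.

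**Working it through.** **1. Where the two windows differ.** Scans come after every second 28-day cycle, so nominally at weeks 8, 16 and so on (protocol Table 2).

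| Scan sequence on treatment | Until-progression window | Any-time window |
|---|---|---|
| PR, then PD | responder | responder |
| PD, then PD (confirmed) | not a responder | not a responder |
| PD, no later scan | not a responder | not a responder |
| PD, then CR or PR; first PD scan is progression (11.2.1/11.2.2) | not a responder | responder |
| PD, then CR or PR; unconfirmed PD is not progression | responder | responder |

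Only the fourth row diverges. The fifth removes the conflict, but no sentence states that rule. The mirror case, a response first seen after treatment ends, is set aside because Table 2 schedules no tumor measurement at follow-up.

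The fourth row also breaks DOR. SAP 3.4 starts from the earliest date of progression, censoring or death, subtracts the earliest response date and adds 1. With PD at week 8 (day 56) and PR at week 16 (day 112), that is 56 − 112 + 1 = −55 days.

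**2. One patient at the thresholds** (Clopper-Pearson 95% intervals, as in SAP 7.1).
- 0/12 (0 to 26.5%), stop; 1/12 = 8.3% (0.2 to 38.5%), continue.
- 2/21 = 9.5% (1.2 to 30.4%), reject; 3/21 = 14.3% (3.0 to 36.3%), consider further.

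**3. The plan's own figures.** Inputs from protocol 14.2: stage I n = 12, total 21, null rate 0.05, alternative 0.20.

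P(go) = Σ over x₁ = 1..12 of Bin(x₁; 12, p) × P(X₂ ≥ 3 − x₁; 9, p)

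At p = 0.05:
- Early termination = 0.95¹² = 0.5404; expected N = 12 + 9 × (1 − 0.5404) = 16.14.
- x₁ = 1: 0.3413 × 0.0712 = 0.0243.
- x₁ = 2: 0.0988 × 0.3698 = 0.0365.
- x₁ ≥ 3: 0.0196.
- P(go) = 0.0804.

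At p = 0.20, P(go) = 0.8033, so the type II error is 0.1967. These match the stated 0.54, 16.14, 0.080 and 0.197. There is no arithmetic error in the design figures.

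**4. Size of the gap between readings.** The documents give no rate q for a first PD scan followed by an on-treatment CR or PR, so q is assumed. With an until-progression ORR of 5%, the any-time rate is 5% + q.

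| q (assumed) | Any-time rate | P(go) |
|---|---|---|
| 0 | 5% | 0.080 |
| 1% | 6% | 0.122 |
| 2% | 7% | 0.170 |
| 3% | 8% | 0.223 |

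In simulation (400,000 trials per setting), the two counts gave opposite final decisions in about 4%, 9% and 14% of trials at q = 1%, 2% and 3%. With an until-progression ORR of 20%, the figures were about 3%, 5% and 7%.

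**The case against.** The best answer is that Section 11.0 opens the chapter, announces an exception for PD, and so governs 11.2.1 and 11.2.2 beneath it. On that reading unconfirmed PD is not progression, and both windows count the later response. The any-time sentence would then mean only that any single on-treatment scan is enough. This is a natural reading and may be what was intended. It is not written down. Section 11.0 dates confirmed PD and is silent on unconfirmed PD; the Table 8 footnote requires confirmation only for new lesions or suspected flare and cites sections that hold no such rule; and SAP 7 uses the category entered in the eCRF at each assessment, where the first scan is PD.

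Three further points stand.
- The case is probably uncommon. Table 8 scores any new lesion as PD, so a PR after new-lesion PD requires that lesion to have gone.
- A reader might infer that 8.2.2 contradicts 11.0. Because 8.2.2 refers to 11.0, it can be read as subject to it. The two need consistent wording, and no view is taken here on which treatment rule is right.
- A reader might infer that CBR is inflated by patients whose PD was never confirmed. No sentence treats them as progression-free, their PD is entered in the eCRF, and SAP 7.2 makes CBR descriptive. No size can be given.

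**Conclusion.** The point holds within a narrow scope. SAP 7.1 contains two windows for the primary numerator, and they disagree for a patient with an unconfirmed PD scan followed by an on-treatment CR or PR if PD is taken on a single scan. One such patient can reverse the stage I or the final decision. That result needs no assumption about frequency.

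A reader might go further and infer that the trial's type I error is really 0.122 to 0.223. The documents do not support that. The 1% to 3% is assumed, and whether these patients are false responders depends on the definition of progression that the plan has left open. If unconfirmed PD is declared not to be progression, the same patients stay in the numerator. The figures show how far apart the readings can be, not inflation that a clearer rule would remove. What is gained is a single rule fixed before the results are known.

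**What to change.** 1. In SAP 7.1, define ORR as the proportion of patients whose best overall response is CR or PR, within the until-progression window, and delete the any-time wording. Tables 05.01 and 05.02 then agree by construction.
2. State once, for ORR, CBR and DOR, whether progression means the first PD scan under RECIST 1.1, the criterion named in protocol 3.1, or PD confirmed under 11.0. Count a PD scan with no later scan as PD on that date. Section 11.0 does not contain this rule, so it has to be added.
3. List every responder whose CR or PR followed a PD scan, and give ORR and the go/no-go result with and without them.
4. Correct the Table 8 cross-reference, reconcile its mandatory confirmation with the optional continuation in 11.0, and make the wording of 8.2.2 consistent with 11.0.

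The cost is a few sentences in a SAP still marked as a draft and a short protocol clarification. The downside is that, if the first-scan definition is chosen, an apparent response after a PD scan will not count in the primary ORR; item 3 keeps it visible.

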7.2 Secondary Efficacy Analyses

The secondary endpoints will be analyzed with a descriptive intent only. The secondary objectives for stage II of the study will be analyzed separately on the ITT population.

7.2.1 Clinical Benefit Rate

CBR is defined as the proportion of patients with no progression or death at 16 weeks.

The 95% confidence interval of the CBR will be reported using exact method based on the binomial distribution (Clopper-Pearson method). The denominator will be the number of patients in the ITT population.

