7.2.4 Targeted therapy

While on study, administration of targeted therapy for malignancy is prohibited.

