12.4 Investigator-initiated discontinuation of study therapy

In addition to the conditions outlined in the protocol, the investigator may require a patient to discontinue study therapy if one of the following occurs:

- the patient develops a serious side effect that cannot be tolerated or that cannot be controlled with other medications,
- the patient's health gets worse,
- the patient is unable to meet the study requirements, or
- new information about the study drugs or other treatments for colon cancer becomes available.

If study therapy is stopped, study data and other materials should be submitted according to the study schedule unless the patient withdraws consent from the study or until there is a diagnosis of a secondary malignancy.

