12.5 Patient-initiated discontinuation of study therapy

Even after a patient agrees to take part in this study, the patient may stop study therapy at any time. If study therapy is stopped, no new therapy begins and the patient still allows the study doctor to submit information, study data and other materials should be submitted according to the study schedule ([Table 2](#)).

12.6 **Patient-initiated withdrawal from the study**

If a patient chooses to have no further interaction regarding the study, the investigator must provide DSSM with written documentation of the patient's decision to fully withdraw from the study. Any data collected up to the time of withdrawal from the study will continue to be used.

13.0 **DATA HANDLING AND RECORDKEEPING**

Refer to the "FC-9 eCRF Completion Guidelines" for detailed instructions regarding data collection, AE reporting, and electronic case report form completion.

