14.2 Statistical design and sample size analysis

The optimal two-stage design ([Simon 1989](#)) to test the null hypothesis that $ORR_0 \leq 0.05$ versus the alternative that $ORR_A \geq 0.20$ has an expected sample size of 16.14 and a probability of early termination of 0.54. If the combination study therapy is actually not effective, there is a 0.080 probability of concluding that it is (the target for this value was $\alpha = 0.10$). If the combination study therapy is actually effective, there is a 0.197 probability of concluding that it is not (the target for this value was $\beta = 0.20$).

Patients who complete both Cycle 1 and Cycle 2, and undergo the first restaging scan after Cycle 2 for the determination of tumor response will be determined as evaluable. Non-evaluable patients will be replaced.

After testing the study therapy combination on 12 evaluable patients in the first stage, the trial will be terminated if 0 patients respond. If the trial goes on to the second stage, a total of 21 evaluable patients will be studied. If the total number responding is less than or equal to 2, the combination is rejected. If 3 or more responses are observed ($ORR \geq 14.3\%$) after the second stage of the study, the combination will be considered for further study.

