2.3 Sample Size Justification

The hypothesis tested to determine the activity of Dual Immune Checkpoint Blockade with Durvalumab plus Tremelimumab expressed in terms of ORR:

H₀: ORR < 0.05

H_A: ORR > 0.20

With the specified null and alternative hypotheses, a type I error rate of 0.10 one-sided and power of 0.80 to reject H₀ if the true response rate is 20%, a Simon two stage design consists of initially treating 12 evaluable patients. Enrolment should end for an inadequate response (futility) if no patients have an objective response. If at least one patient has an objective response, enrolment continues to a total of 21 patients. If at least 3 responses are seen (ORR > 0.143), the treatment will be considered worth testing further.

3. General Analysis Definitions

Data will be analyzed using SAS v 9.4.

Descriptive statistics will be tabulated as follows:

- Categorical data will be summarized in contingency tables presenting frequencies and percentages.
- Continuous data will be summarized using number of non-missing values (n), mean, standard deviation, median, minimum and maximum values.

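### The SAP's 16-week clinical benefit rate has no rule for new anti-cancer treatment, so a patient who switches after the week-8 scan can be credited to the study regimen; duration of response and best overall response also need a stated rule

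*Combined protocol and SAP*

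**What the plan says.** **Clinical benefit.** SAP 7.2.1: "CBR is defined as the proportion of patients with no progression or death at 16 weeks". The denominator is the SAP's ITT population, which SAP 3.3.1 defines as patients who completed Cycles 1 and 2 and had the restaging scan after Cycle 2. Protocol 3.2.1 words the endpoint differently, as tumour measurement showing PR, CR or SD at 16 weeks. SAP 3.5 states that nothing was changed from the protocol's planned analyses.

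**Duration of response.** SAP 3.4 and 7.2.2 end it at progression, censoring or death. Neither says what triggers censoring.

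**Response.** Protocol 11.2.3, repeated in SAP 7.1: "The best overall response is the best response recorded from the start of the treatment until disease progression/recurrence". The next paragraph of SAP 7.1 is narrower and counts a CR or PR for ORR only if it occurs during treatment.

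**Other treatment.** Protocol 8.2.2 lists among the reasons for stopping study therapy: "Initiation of alternate cancer therapy including another investigational agent". Protocol 7.2.4 adds: "While on study, administration of targeted therapy for malignancy is prohibited". No section addresses non-study local treatment by name.

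**Data after stopping.** Protocol 12.4, for an investigator's decision: "If study therapy is stopped, study data and other materials should be submitted according to the study schedule unless the patient withdraws consent". Protocol 12.5, for a patient's decision, sets a condition: "If study therapy is stopped, no new therapy begins and the patient still allows the study doctor to submit information". A cut-off at new therapy is written only for adverse events (Table 2 footnote d, Protocol 10.8, SAP 3.1.1).

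**The concern.** In a single-arm trial every patient without progression at week 16 is attributed to the regimen, and no control group shares the bias if some were by then on something else. The authors foresaw switching, since adverse-event collection ends there, but wrote no matching rule for efficacy.

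What is at stake is the meaning of CBR, which would mix the regimen's effect with that of its successor. Reproducibility is also at stake: two analysts could handle a switch differently for DOR and report different medians from the same data. And because 12.4 and 12.5 differ, the information available on a switcher depends on who decided to stop.

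**Working it through.** **1. The plan's own figures.** The plan gives no expected CBR. Its design figures rest on ORR alone. Inputs from Protocol 14.2 and SAP 2.3: null rate 0.05, alternative 0.20, 12 then 21 evaluable patients, stopping after Stage I with no response ("the trial will be terminated if 0 patients respond"), and 3 or more responses needed at the end.
- Early stopping at the null: 0.95^12 = 0.540 (stated 0.54).
- Expected size: 12 + 9 × (1 − 0.540) = 16.14 (stated 16.14).
- Chance of success at rate p: the sum over x = 1 to 12 of P(X1 = x; 12, p) × P(X2 ≥ 3 − x; 9, p). At 0.05 this is 0.0804 (stated 0.080). At 0.20 it is 0.8033, so the miss probability is 0.1967 (stated 0.197).

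All four reproduce. CBR enters none of them, so correcting it leaves the sample size and decision rule unchanged.

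**2. The exposure window.** A cycle is 28 days. Two cycles are 56 days (week 8) and four are 112 days (week 16). A patient who misses the scan after Cycle 2 is non-evaluable and replaced. The gap therefore concerns evaluable patients who stop between about week 8 and week 16, if there are no delays.

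**3. One patient under both definitions.** Take stable disease at week 8, a toxicity stop in Cycle 3, another agent started in week 12, and no progression or death recorded by week 16.
- SAP 7.2.1: no progression and no death, so clinical benefit.
- Protocol 3.2.1, reading the 16-week condition as applying to CR, PR and SD alike: benefit only if a tumour measurement supports it. Table 2's follow-up column marks no target-lesion measurement, so there may be none. If there is one, it reflects the new agent.

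Sparse imaging after stopping does not protect the SAP version, because that version is defined by absence of an event.

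**4. Size.** If k patients are credited this way among 21, CBR rises by k/21: 4.8 percentage points for k = 1 and 9.5 for k = 2. The values of k are assumptions. As an illustration with exact 95% limits, 5/21 = 23.8% (8.2% to 47.2%) becomes 6/21 = 28.6% (11.3% to 52.2%). The shift is small beside the interval, but it goes in one direction only.

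**5. ORR.** SAP 7.1 counts responses during treatment, and Protocol 8.2.2 ends treatment when alternate cancer therapy begins. Together they exclude a response first seen after a systemic switch. Protocol 1.0 also confines response to unirradiated target lesions. Two gaps remain. The best-overall-response sentence runs to progression with no such end, and it feeds SAP Table 05.01. Non-radiation local treatment of a target lesion, such as ablation or resection, is not mentioned. Protocol 4.1.9 requires only one unirradiated RECIST lesion, and SAP 7.1 does not require confirmation of response.

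**6. DOR.** With censoring allowed but undefined, new therapy is neither a named end point nor ruled out as one.

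**The case against.** The strongest defence is that the secondary endpoints are descriptive (SAP 7.2) and drive no decision, that Table 2 schedules no tumour measurement after stopping, and that the protocol's CBR already needs measured disease status. The first part stands and limits the consequence. The second does not help, for the reason in step 3. The third shows the protocol is sounder than the SAP, but the SAP is what will be programmed.

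Several stronger readings are tempting, and the documents do not support them:
- A reader might infer that the primary endpoint counts responses to later systemic therapy and that the type I error is inflated. Step 5 shows the ORR wording excludes them. Any inflation figure would have to assume a false responder whose frequency the documents do not give.
- A reader might infer from 7.2.4 that everything except targeted therapy is allowed. Protocol 8.2.2 makes alternate cancer therapy incompatible with continued study therapy and is not limited to drugs. The list in 4.2.24 is an entry washout list, not a permission on study. It includes one local treatment, embolization, and needs a note to exempt the protocol SBRT.
- A reader might project the toxicity discontinuations of the combination study in Protocol 2.5 onto this trial. Those were lung cancer patients across all dose cohorts. They are not shown to have stopped between weeks 8 and 16, without progression, or to have gone on to new therapy.
- A reader might say that DOR ignores new therapy. It provides for censoring and leaves the events undefined.

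It is also fair that scoring switchers as non-benefit is one defensible choice among several. The plan states none, and this choice fits a claim about the study regimen.

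**Conclusion.** The concern holds for CBR. As written, SAP 7.2.1 credits the study regimen with any evaluable patient who switches treatment between the week-8 scan and week 16 and has no recorded progression or death. It is also looser than Protocol 3.2.1. Each such patient is worth 4.8 percentage points, assuming the full 21 evaluable patients; how many there would be cannot be estimated from the documents. DOR has an undefined censoring rule. For ORR the remaining gap is narrow: a best-overall-response window wider than the ORR sentence, and silence on non-study local treatment of a target lesion. The plan should be corrected, but the two-stage decision rule and its error rates are not called into question.

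**What to change.** - **SAP 7.2.1:** require CR, PR or SD at the week-16 assessment. Count patients who start new systemic anti-cancer therapy, or have non-study local treatment of a target lesion, before that assessment as not having clinical benefit.
- **SAP 7.1 and Protocol 11.2.3:** end the best-response window at the start of such treatment, to match the ORR sentence.
- **SAP 7.2.2:** censor DOR at the last tumour assessment before such treatment.
- **Data:** make sure the type, site and start date of such treatment are recorded. The eCRF is not among the documents, so first check whether it already holds them.
- **Protocol 12.4 and 12.5:** reconcile them without ending collection of progression and death data. Simply extending the no-new-therapy condition of 12.5 to 12.4 would lose that information.

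The cost is wording in the SAP, which is still marked as a draft, a few protocol sentences and perhaps a small addition to data capture. Sample size and treatment rules do not change. The downside is that CBR may be slightly lower.
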